Discontinue recrutiment in investigational arm 2 (PM 14d / MF 28 days). Following review of the preliminary available data by the DSMB, including 143 study participants enrolled, among which 135 had completed treatment and Day 28 assessment, and 66 of them had completed their day 210 follow-up visit, it was decided in agreement with the DSMB to ensure retention of the investigational arm 1, on the basis of 1) shorter treatment duration than current standard of care, 2) it can be administered within the hospitalisation period, 3) it is a cheaper option for the control programs, and therefore from a public health perspective will be a potentially more favorable option for patients.

Confidential Page 21 of 68

In this revised protocol version, the analysis remains as planned, but comparison will be performed only between one investigational arm (arm 1 MF/PM 14 days) and the standard of care (SSG-PM). Data from patients randomized in arm 2 (PM 14 days/MF 28 days), which recruitment is now stopped, will be summarized in a descriptive analysis, but will not be included in the comparative hypothesis testing.

The total dose of PM will be 280 mg, similar to the total dose given in the SSG-PM combination therapy (255 mg). For MF, PK data indicated that with 14 days allometric MF treatment, 91% of patients will at least reach EC90 in plasma, which would represent appropriate exposure.

If demonstrated non-inferior to SSG-PM, the 14-day MF-PM regimen will be preferable to be taken forward for future standard of care or alternative treatment to SSG-PM. Data will be presented to Ministry of Health (MoH) and regulatory authorities in the region as evidence to support policy change for the national control programs.

2. Study Objectives and Endpoints

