3.1. Study design

This is an open label, Phase III, randomized, controlled, parallel arm multicentre non-inferiority clinical trial to compare the efficacy of a combination regimen of MF and PM with SSG-PM for the treatment of primary adult and children VL patients in Eastern Africa.

In addition, safety of two combination regimens of PM (14 days) and MF (14 or 28 days) will be assessed, and the efficacy of the PM (14 days) and MF (28 days) investigational arm 2 will be described.

The study will be conducted at 5 LEAP sites and 2 MSF sites: Kacheliba in Kenya,

Confidential Page 23 of 68

Amudat in Uganda, Doka, Um El Kher and Tabarakallah (MSF) in Sudan and Gondar and Abdurafi (MSF) in Ethiopia.

The 2 treatment regimens to be tested were as below but with patient's recruitment in arm 2 now discontinued:

- Arm 1: Paromomycin 20 mg/kg/d IM for 14 days combined with oral miltefosine allometric dosing for 14 days
- Arm 2: Paromomycin 20 mg/kg/d IM for 14 days combined with oral miltefosine allometric dosing for 28 days (recruitment is now discontinued in this arm but patients' data available will be analyzed and results described)

The reference arm is the current standard treatment for VL:

Arm 3: Sodium Stibogluconate 20 mg/kg/day IM/IV combined with Paromomycin 15 mg/kg/day IM for 17 days

For patients weighing < 30 kg, an easy-to-use table with allometric dosing scheme by weight, height and sex will be provided to the investigators to define the exact daily dose to be administered. For patients weighing \geq 30 kg, the allometric dose will correspond to the conventional dose in mg/kg. Therefore, in order to simplify the dose calculation, patients weighing \geq 30 to < 45 kg will receive 100 mg/day and patients \geq 45 kg will receive 150 mg/day.

The target population will be VL patients from 4 to 50 years old in order to cover both paediatric and adult population. The limit of 50 years for inclusion is due to higher mortality rate and lower efficacy observed in patients > 50y when treated with SSG-PM in a recent pharmacovigilance program (Kimutai et al., 2017). MF and PM will be administered together, both starting at D1. PM dosage will be 20 mg/kg/d for 14 days administered once-a-day intramuscularly, whereas MF allometric dose will be administered orally BID for 14 days in arm 1 and for 28 days in arm 2.

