7.1. DNDi study treatment

Name: Miltefosine (Impavido®)

Class: Phosphocholine analogue.

Mechanism of action: interferes with the synthesis and metabolism of phospholipids.

It may also interfere with the parasite's membrane signal transduction, and

glycosylphosphatidylinositol anchor biosynthesis.

Commercial source: Paladin labs and Knight Therapeutics Inc.

Product appearance: comes as 10mg and 50mg capsules in pack of 56 capsules sealed in 8 aluminum blister stripes, each containing 7 capsules.

Administration: oral treatment

For MF, there are no known interactions with other commonly used medications, though this cannot be excluded.

Confidential Page 32 of 68

Name: **Paromomycin** Class: Aminoglycoside

Mechanism of action: inhibits protein synthesis by binding to 16S ribosomal RNA.

Commercial source: Gland Pharma, India; distributed by IDA Foundation.

Product appearance: Each box of paromomycin contains a pack of 10 amber-colored glass ampoules containing 750 mg of paromomycin base in 2 ml (375 mg/ml) equivalent to 1 g of paromomycin sulphate in 2 ml (500 mg/ml).

The 20 mg/kg sulfate is equivalent to 15 mg/kg of base.

Administration: intramuscular injection.

Name: Sodium Stibogluconate

Class: Pentavalent antimonial

Mechanism of action: decrease in ATP and GTP synthesis contributes to decreased macromolecular synthesis and to decreased *Leishmania* viability.

Commercial source: Albert David Ltd., India; distributed by IDA Foundation.

Product appearance: A faintly straw coloured fluid in a multi-dose brown opaque vial of 30ml containing SSG BP equivalent to 100mg pentavalent antimony in each ml (total 3g).

Administration: Given IV (slow over 5 minutes) or IM at a daily dose of 20mg/kg body weight.

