7.2. Doses and treatment regimens

7.2.1 Test arms

Arm 1: Paromomycin 20 mg/kg/d IM q.d. for 14 days combined with oral miltefosine allometric dosing b.i.d. for 14 days

Arm 2: Paromomycin 20 mg/kg/d IM q.d. for 14 days combined with oral miltefosine allometric dosing b.i.d. for 28 days (recruitment is now discontinued in this arm)

MF dosing will be defined as follows:

- Patients <30 kg: the allometric MF daily dose will be calculated according to subject's weight, height and sex
- Patients ≥ 30 to <45 kg: 100 mg/day
- Patients ≥ 45 kg: 150 mg/day

PM and MF will be administered together, both starting at D1. PM dosage will be 20 mg/kg/d for 14 days administered intramuscularly, whereas MF allometric dose will be administered orally for 14 days in arm 1 (it used to be administered for 28 days in arm 2).

Patients are hospitalized for 14 days of PM and MF treatment in both arm 1 and arm 2. The MF treatment will start at the same time as the PM treatment and for arm 2 it used to continue on an out-patient basis until completion of the 28 days treatment.

Miltefosine administration

MF will be administered orally for 14 days in arm 1 and used to be administered for 28 days in arm 2.

Confidential Page 33 of 68

For patients less than 30 kg, the allometric dose will be defined according to weight, height and sex as indicated in Table 1, divided in 2 administrations per day for 14 days in arm 1 or 28 days in arm 2 (not applicable now recruitment has been discontinued in arm 2).

Table 1 - Daily allometric miltefosine dose for female children based on fat-free mass

FEMALE									
HT (cm)	80-89	90-99	100-109	110-119	120-129	130-139	140-149	150-159	160
WT (kg)									
7									
8	30								
9	30			RISK (OF SF\	/FRF N	ΛΑΙ ΝΙ	JTRITI	ON
10		40		111011		THE WHO F			
10	30	40	40		KEFEK IU	THE WHO F	KEFEKENCE	CURVES	
	40		40 40						
12 13	40 40	40 40	40						
14	40	40	40	50					
15	40	40	50	50					
16	40	50	50	50					
17	40	50	50	50	50				
18	50	50	50	50	60				
19	50	50	50	60	60				
20	50	50	50	60	60				
21	50	50	60	60	60	60			
22	50	50	60	60	60				
23	50	50	60	60	60		70		
24	50	50	60	60	60	70	70		
25	50	60	60	60	70		70		
26	50	60	60	60	70		70	70	
27	50	60	60	70	70		70	80	
28	50	60	60	70	70	70	80	80	
29	50	60	60	70	70		80	80	
30	50	60	60	70	70	80	80	80	80

Confidential Page 34 of 68

Table 2 - Daily allometric miltefosine dose for male children based on fat-free mass

MALE									
HT (cm)	80-89	90-99	100-109	110-119	120-129	130-139	140-149	150-159	160

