Patients in arm 2 used to continue MF intake after discharge at day 14 on an outpatient basis. Compliance during the 14 days treatment outside the hospital was assessed by collecting the empty blisters at the day 28 visit and checking for any unused drug. A diary including illustrations that is made understandable for illiterate subjects was provided to these patients in order to guide them in their treatment schedule at home. Any episode of vomiting reported by the patient was captured by the clinician at day 28 visit. In case of multiple episodes of vomiting, patients were instructed to come to the hospital for an assessment in an unscheduled visit. Compliance will be further assessed through cross-check with PK data.

Paromomycin administration

PM will be given for 14 days in both arm 1 and arm 2. Exact daily dose of 20 mg/kg will be calculated using patient's body weight and will be administered once-a-day with intramuscular injection into the buttock muscle.

PM sulfate will be supplied through IDA Foundation, Holland, in boxes of 10 amber-colored glass ampoules each, containing an equivalent 750 mg of PM base in 2 ml (375 mg/ml).

All administrations will be directly observed by the study nurse or clinician to assure compliance.

Treatment interruption

MF treatment in arm 1 (14 days) will last at least 13 days in order to be considered 90% compliant. In case of treatment interruption longer than 24 hours, missing doses will be compensated after day 14.

MF treatment in arm 2 (28 days) could be temporarily interrupted (due to AEs or at discretion of investigator) and resumed if this interval was no longer than 72hs. In this case, the total administered dose over a total of 25 days was still considered within 90% range of full compliance, therefore it was not considered a compliance deviation. The missing doses was not compensated after the final dose on day 28, and the

Confidential Page 36 of 68

schedule of assessments would remain the same.

If treatment needs to be interrupted for > 72hs due to an AE related to MF, or if treatment needs to be interrupted due to an AE related to PM or SSG, rescue treatment will be considered, at the discretion of the investigator.

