7.2.2 Reference arm

Arm 3: Sodium Stibogluconate 20 mg/kg/day Intravenous/Intramuscular (IV/IM) q.d. and Paromomycin 15 mg/kg/day IM q.d. for 17 days

SSG will be given IM/IV at a dose of 20 mg/kg once daily for 17 days. PM base will be administered IM at a dose of 15 mg/kg once daily for 17 days. The dosing regimen will be the combination of both SSG and PM as described above.

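### The paromomycin doses of the two compared arms are not given on a stated common salt basis, and if arm 1's 20 mg/kg is sulfate, either the background dose comparison or the arm 3 dosing line is wrong

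*Combined protocol and SAP*

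**What the plan says.** **Arm 1.** Every dosing statement gives 20 mg/kg/day for 14 days and names no salt. This holds for the regimen line in the protocol summary, section 3.1 ("PM dosage will be 20 mg/kg/d for 14 days administered once-a-day intramuscularly") and section 7.2.1 ("PM dosage will be 20 mg/kg/d for 14 days administered intramuscularly", and under paromomycin administration "Exact daily dose of 20 mg/kg will be calculated"). Section 7.2.1 then says that the sulfate is supplied, but gives the ampoule strength only as base: "containing an equivalent 750 mg of PM base in 2 ml (375 mg/ml").

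**Arm 3.** Section 7.2.2 names the basis: "PM base will be administered IM at a dose of 15 mg/kg once daily for 17 days".

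**Conversion.** The product description in section 7.1 gives the ampoule both ways, as 375 mg/ml base and 500 mg/ml sulfate, and adds: "The 20 mg/kg sulfate is equivalent to 15 mg/kg of base". It ties this line to no arm.

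**Comparison of totals.** Section 1 (Background and Study Rationale) states: "The total dose of PM will be 280 mg, similar to the total dose given in the SSG-PM combination therapy (255 mg"). No salt is named. The same section treats 20 mg/kg as an increase over 15 mg/kg, prefers it because it permits a shorter course, and says that efficacy follows cumulative exposure.

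**Use of the result.** If non-inferiority is shown, "Data will be presented to Ministry of Health (MoH) and regulatory authorities in the region" to support policy change.

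**The concern.** The only place that attaches a salt to 20 mg/kg calls it sulfate, and the only place that attaches a salt to arm 3's 15 mg/kg calls it base. Taken together, the two arms would receive the same daily amount of paromomycin. That does not fit the background section, which treats the two doses as different levels and compares their totals as like with like.

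The basis decides how much of an aminoglycoside is injected, and section 1 lists reversible ototoxicity among its reported effects. The same arm 1 instruction gives volumes that differ by a third, depending on which of the protocol's two ampoule strengths is used. The basis also decides whether arm 1's daily paromomycin dose equals arm 3's or is a third higher, which a reader needs to know when comparing safety between the arms. A regimen offered to health ministries should have a dose that can be reproduced from the protocol.

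**Working it through.** **Inputs**
- Arm 1: 20 mg/kg/day for 14 days, salt not named (3.1, 7.2.1).
- Arm 3: 15 mg/kg/day for 17 days, base (7.2.2).
- Ampoule: 375 mg/ml base = 500 mg/ml sulfate (7.1).

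**Step 1: the plan's own totals.** 20 × 14 = 280 and 15 × 17 = 255, so both figures reproduce. The ratio is 280/255 = 1.098, so arm 1 is 9.8% higher. The products are in mg/kg, although section 1 prints mg. At 30 kg a single day's arm 1 dose is 20 × 30 = 600 mg, already above the printed 280 mg for the whole course.

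**Step 2: conversion.** Base/sulfate = 375/500 = 15/20 = 0.75. The ampoule strengths and the line in 7.1 agree.

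**Step 3: common basis (mg/kg base).**
- *A. Arm 1 sulfate, arm 3 base as written.* Arm 1: 20 × 0.75 = 15 per day, × 14 = 210. Arm 3: 15 × 17 = 255. Ratio 210/255 = 0.824.
- *B. Both sulfate.* Arm 1: 210. Arm 3: 15 × 0.75 = 11.25 per day, × 17 = 191.25. Ratio 210/191.25 = 1.098.
- *C. Both base.* Arm 1: 20 × 14 = 280. Arm 3: 255. Ratio 280/255 = 1.098. Arm 1 expressed as sulfate: 20/0.75 = 26.7 mg/kg/day.

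| Reading | Course total, arm 1 vs arm 3 (mg/kg base) | Arm 1 relative to arm 3 | Daily dose ratio | What fails |
|---|---|---|---|---|
| A | 210 vs 255 | −17.6% | 15/15 = 1.00 | Comparison in section 1 mixes bases |
| B | 210 vs 191.25 | +9.8% | 15/11.25 = 1.33 | The word base in 7.2.2 |
| C | 280 vs 255 | +9.8% | 20/15 = 1.33 | No sentence, but 7.1 shows 20 mg/kg only as sulfate |

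**Step 4: effect of following the text.** Under B, a site that gives 15 mg/kg base in arm 3 gives 15/11.25 = 1.33 times the intended dose. Under C, a site that takes 7.1 to mean 20 mg/kg sulfate in arm 1 gives 15/20 = 0.75 of the intended dose.

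**Step 5: volume per injection.** Arm 1: 20/500 = 0.040 mL/kg as sulfate, or 20/375 = 0.053 mL/kg as base. Arm 3: 15/375 = 0.040 mL/kg as base, or 15/500 = 0.030 mL/kg as sulfate. At 30 kg, arm 1 is 1.2 or 1.6 mL and arm 3 is 1.2 or 0.9 mL.

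**The case against.** The strongest reply is reading C. If both doses are base, the ratio in section 1 holds, 7.2.2 is right, and 7.1 is simply a correct conversion that ends at arm 3's dose. The base-only ampoule strength in 7.2.1 fits this too. Reading B, by contrast, needs an explicit word in 7.2.2 to be wrong. This stands: the documents permit a reading with no contradiction. It does not settle the matter, because 7.1 speaks of the 20 mg/kg dose as sulfate, and arm 1 is the arm with that dose.

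The second reply is that other materials may fix the basis. Arm 3 follows routine treatment guidelines at centres that treat this disease regularly, a package insert is cited, and section 7.3 puts directions for use on the label. None of these is shown. They could settle practice at the bedside, but they would not repair a wrong line in section 1 or 7.2.2.

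A reader might also infer several stronger things that the documents do not support:
- *That patients were misdosed.* Nothing shows what was injected.
- *That arm 1 receives 17.6% less paromomycin than control.* This arises only under A. Section 1's treatment of 20 mg/kg as an increase over 15 mg/kg suggests one common basis, which counts against A.
- *That the 90–110% compliance rule in section 10.5 fails.* The rule divides the dose administered by the dose prescribed, so the ratio is unaffected when both use the same basis. Nothing suggests that they differ.

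**Conclusion.** The gap is real and should be corrected. Arm 1's salt basis is not stated, and the two statements nearest to it (7.1 for 20 mg/kg, 7.2.2 for 15 mg/kg) use different bases.

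The size depends on the reading. If arm 1 is sulfate, either the section 1 comparison is wrong (210 against 255 mg/kg base, with identical daily doses) or 7.2.2 sets the control dose 33% above the intended 11.25 mg/kg base. If both doses are base, the text is consistent, but 7.1 invites a 25% under-dose in arm 1. The preference for a common basis in section 1 favours B or C over A. That is an inference from how the background discusses the doses, not a stated fact, and the documents do not settle which reading applies.

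The calculation assumes only the protocol's own conversion factor of 0.75. The non-inferiority test, margin, alpha and sample size do not depend on it. The mg printed for mg/kg in section 1 is a clerical slip, since the dosing instructions themselves are in mg/kg.

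**What to change.** 1. In sections 3.1, 7.2.1 and 7.2.2, state for each arm whether the paromomycin dose is sulfate or base, and give the mL/kg of the supplied ampoule (375 mg/mL base = 500 mg/mL sulfate).
2. Correct whichever of the section 1 comparison or the word base in 7.2.2 is wrong. If both doses are base, say in 7.1 that the conversion line refers to arm 3.
3. Restate the section 1 totals in mg/kg on one named basis.
4. Confirm that the label directions agree.
5. Check the recorded doses for the basis used, by site and arm.

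Items 1 to 4 are wording changes and a label check. Item 5 is a small extra task: section 10.5 requires the dose to be recorded, but does not call for this review or say that the salt basis is recorded. There are no added patient procedures and no change to the design or sample size.

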2.1.2. Secondary Objectives

- To assess the safety of two combination regimens of PM (14 days) and MF (14 or 28 days) with the standard 17-day course of SSG-PM
- To describe the efficacy of the PM (14 days) and MF (28 days) investigational arm
- To describe the pharmacokinetic (PK) profiles of PM and MF (14 days and 28 days regimen) in primary VL patients
- To evaluate parasite clearance in each arm as indicated by direct microscopy and quantitative polymerase chain reaction (qPCR)
- To assess the relationship between PK and PD measurements (parasitological and clinical outcome)
- To describe compliance to MF treatment in an outpatient setting

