WT (kg)									
7									
8	40								
9	40			RISK (OF SE\	/ERE N	/ALNU	JTRITI	ON
10	40	40			REFER TO	THE WHO F	REFERENCE	CURVES	
11	40	40							
12	40	50							
13	50	50	50						
14	50	50	50						
15	50	50	60	60					
16	50	50	60	60					
17	50	60	60	60					
18	50	60	60	60	70				
19	50	60	60	70	70				
20	50	60	60	70	70				
21	60	60	60	70	70	70			
22	60	60	70	70	70	80			
23	60	60	70	70	80	80			
24	60	60	70	70	80	80	80		
25	60	60	70	70		80	80		
26	60	70	70	80	80	80	100		
27	60	70	70	80	80	80	100		
28	60	70	70	80	80	100	100	100	
29	60	70	70	80	80	100	100	100	
30	60	70	80	80	100	100	100	100	

MF 10 mg and 50 mg strengths will be supplied through MSF Supply, Belgium, and Knight Therapeutics, US respectively in alu/alu blister packs of 56 capsules.

Administration of the daily dosage must be divided in 2 administrations, during or after a meal, to avoid direct gastrointestinal adverse effects of MF, as follows:

Total daily dose, divided:	30mg	40mg	50mg	60mg	70mg	80mg	100mg	150mg
Morning (breakfast)	2x 10mg	2x 10mg	1x 50mg	1x 50mg	1x 50mg	1x 50mg	1x 50mg	2x 50mg
Afternoon (dinner)	1x 10mg	2x 10mg		1x 10mg	2x 10mg	3x 10mg	1x 50mg	1x 50mg

Confidential Page 35 of 68

During the 14 days of hospitalization, administrations for all patient's arms will be directly observed by the study nurse to assure compliance. The number of capsules administered (morning and afternoon), the time of administration and any vomiting episode will be documented in a patient dispensing log. After each drug intake the patients will be observed for vomiting for 30 minutes. All vomiting episodes will be recorded. In case of vomiting within 30 minutes after intake, the dose will be readministered. If a repeated vomiting occurs (vomiting after re-dose) the treatment will not be re-administered.

Compliance will be assessed by total dose taken by the patient. Full compliance will be considered if 90-110% of the prescribed dose is administered.

If the patient vomits a dose within 30min of drug intake and is re-dosed (without vomiting this 2nd re-dose), the re-dose will be considered for compliance. However, if the patient is not re-dosed within 30min or if s/he vomits the re-dose, this dose will not be accounted for compliance. In the case of a patient vomiting after 30min of MF intake, the dose will be accounted for compliance.

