10.5. Treatment Compliance

All test drugs will be supervised on administration by study medical staff. The dose given will be recorded in the patient dispensing log and in the CRF. Full compliance will be considered if 90-110% of the prescribed dose is administered.

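### Section 7.2.1 treats 25 of 28 days of miltefosine in arm 2 as meeting the 90% compliance limit, but 25/28 is 89.3%

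*Combined protocol and SAP*

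**What the plan says.** All references are to the combined protocol and SAP.

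Section 7.2.1, under miltefosine administration, sets the measure: "Compliance will be assessed by total dose taken by the patient". The limit is given there and again in section 10.5: "Full compliance will be considered if 90-110% of the prescribed dose is administered".

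Section 7.2.1, under treatment interruption, then gives a rule for each arm:

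- **Arm 1 (14 days).** Treatment "will last at least 13 days in order to be considered 90% compliant".
- **Arm 2 (28 days).** Miltefosine could be paused, because of adverse events or at the investigator's discretion, and "resumed if this interval was no longer than 72hs". The rule then says that "the total administered dose over a total of 25 days was still considered within 90% range of full compliance", and concludes: "therefore it was not considered a compliance deviation". Missed doses were not made up: "The missing doses was not compensated after the final dose on day 28".

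**The concern.** The arm 2 rule rests on a numerical claim, and that claim does not agree with the limit set in the same section. A patient who missed three full days would be within the 90% range under the interruption rule, but not fully compliant under the total-dose definition in sections 7.2.1 and 10.5. Two analysts could classify that patient differently, and each could cite the protocol. What is at stake is the classification of whole-course miltefosine compliance in arm 2.

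**Working it through.** **Inputs.** Section 7.2.1 gives the planned durations (14 days in arm 1, 28 in arm 2), the days said to suffice (13 and 25), the 72-hour maximum, and the morning and afternoon split of each daily dose. Sections 7.2.1 and 10.5 give the lower limit of 90% of the prescribed dose. The daily dose is constant over the course, so the fraction of dose equals the fraction of full days taken.

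**The plan's own figures.**

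- Arm 1: 13/14 = 92.9%, which is at least 90%. The statement is reproduced.
- Arm 2: 25/28 = 89.3%, which is below 90%. The statement is not reproduced, and the value rounds to 89%, not 90%.

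**What 90% requires in arm 2.** 0.90 × 28 = 25.2 days' dose. In whole days that is 26, and 26/28 = 92.9%. At most 28 − 25.2 = 2.8 days' dose may be missed, and 2.8 × 24 h = 67.2 h, slightly less than the 72 hours allowed.

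**Size in milligrams.** With 25 full days taken, the shortfall is 25.2 − 25 = 0.2 of a daily dose at every dose level:

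| Daily dose | Taken over 25 days | 90% of the 28-day dose | Short by |
|---|---|---|---|
| 30 mg | 750 mg | 756 mg | 6 mg |
| 60 mg | 1500 mg | 1512 mg | 12 mg |
| 150 mg | 3750 mg | 3780 mg | 30 mg |

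**How the 72 hours are counted.** The protocol does not define this, so each way was checked.

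- *From the first missed dose to the resumed dose.* Six doses are missed (three at 50 mg/day, which is given once daily). The fraction is again 89.3% at every dose level. This matches the protocol's own figure of 25 days.
- *From the last dose taken to the next dose taken.* At most five doses are missed (two at 50 mg/day). Only 60 mg/day can then fall below the limit. If the gap starts after an afternoon dose, the loss is 3 × 50 + 2 × 10 = 170 mg of 1680 mg. That leaves 1510/1680 = 89.9%, 2 mg under the 1512 mg required. If it starts after a morning dose, 60 mg/day keeps 1550/1680 = 92.3%. At the other seven levels the worst case runs from 90.3% (70 mg/day) to 92.9% (50 mg/day).

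**The case against.** The strongest defence is that the sponsor was setting a deliberate tolerance for a clinically permitted pause and was not claiming exact arithmetic. Part of this stands: the sponsor may rule that a pause of up to 72 hours is not a deviation, and that ruling does not depend on reaching 90%. But the text states no tolerance. It gives a numerical reason and draws its conclusion from it with the word *therefore*. Neither section 7.2.1 nor section 10.5 allows a margin around 90%, and the arm 1 rule beside it passes an exact check.

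A second defence is that 72 hours is a maximum and, counted between doses actually taken, nearly always leaves 90% or more. That is correct for the 72-hour permission. It does not rescue the sentence, which speaks of 25 days' total dose.

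A third is that the consequence is close to nil. That is largely right. Recruitment to arm 2 has stopped, and under section 10.2 its data are summarised descriptively, outside the comparative efficacy analysis. No section names an arm 2 full-compliance rate as a planned statistic.

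A reader might go further and infer that the error undermines the secondary objective in section 2.1.2, "To describe compliance to MF treatment in an outpatient setting", because only arm 2 took miltefosine at home. The documents do not support that. The interruption rule covers the whole 28-day course, including the 14 hospital days and pauses caused by adverse events or ordered by the investigator, which are not outpatient non-adherence. Outpatient compliance is assessed separately, from returned blister packs, unused drug, hospital records and PK (sections 7.2.1 and 2.2.2), and nothing applies the 90-110% limit to the outpatient fortnight alone. If that fortnight were the denominator, three missed days would give 11/14 = 78.6%, and the question of 89.3% against 90% would not arise.

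**Conclusion.** The statement is wrong as written. A total dose over 25 of 28 days is 89.3% of the prescribed dose, 0.7 percentage points under the protocol's own limit, and no other section corrects it or supplies a tolerance. The result rests on a constant daily dose and on taking 25 days at face value. If the 72 hours run between doses actually taken, a permitted pause meets 90% in all cases except 60 mg/day interrupted after an afternoon dose.

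This is a minor correction. The effect is limited to the descriptive classification of whole-course miltefosine compliance in discontinued arm 2. The number of patients affected is unknown and may be zero. The arm 1 rule is right, and the arm 1 versus arm 3 comparison is untouched.

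**What to change.** Before database lock, delete from section 7.2.1 the statement that 25 days' dose falls within the 90% range. Classify full compliance in arm 2 only by the existing 90-110% limit on total dose taken. Keep the ruling that a permitted interruption of up to 72 hours is not a protocol deviation, as a rule in its own right that no longer rests on the 90% claim.

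The cost is one line of text. No new data or additional table row is needed, because total dose taken is already the compliance measure. No formal comparison changes.
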